## 5. AMENDMENTS AND UPDATES

Not applicable.

## 6. MILESTONES

Milestone	Planned date
Protocol submission to EMA	by 30 June 2014
Protocol approval by EMA	March 2015 *
Contract signature for study roll-out phase	April 2015*
Registration in the EU PAS register	April 2015*
Start of data collection	April 2015*
Statistical Analysis Plan	May 2015
End of data collection	End of June 2015
PSUR Update 1	October 2015
Start of data collection (second wave)	April 2016
End of data collection (second wave)	End of June 2016
PSUR Update 2	October 2016
Start of data collection (third wave)	April 2017
End of data collection (third wave)	End of June 2017
PSUR Update 3	October 2017
Final report of study results	End of November 2017

*\*Delay will impact the subsequent dates*

Milestones have been planned to maximise the efficiency and availability of data retrieval from the different data sources. A summary of such information is provided here:

Data source (Country)	Periodicity of updates	Time of the year when updates are released	Data availability for each update
SIDIAP (Spain)	Yearly	April-May	End (December 31 st ) of previous calendar year
IPCI (NL)	Yearly (twice is possible)	April-May	Variable as GPs provide not all at same time
THIN (UK)	Three times per year	Irregular	Variable as GPs provide not all at same time
HSD (Italy)	Every 6 months	June and December	End of previous calendar year (in June); up to June in December.
AUH (Denmark)	Yearly	May	December 31st the previous year

Both national regulations and prescribing practices have changed throughout the participating databases in recent months. As a consequence, in Italy, where GPs in primary care are not allowed anymore to initiate or renew strontium ranelate treatment since December 2013, the number of incident strontium ranelate users in the assessment period is expected to be null or very low. This point will be assessed for the first PSUR update (October 2015) as part of the analyses of the utilization patterns at population level (see [section 9.7.2.1](#)).

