### **Study population**

The study population will comprise the entire source population for the measurement of risk minimization effectiveness. It comprises a cohort of new SR and oral bisphosphonate users for the comparative safety study. Specific inclusion and exclusion criteria will apply

Study period: the study period will start in 2004 (2006 for SIDIAP) and end at latest data supply. This period will be split in three analysis periods for the analysis of effectiveness of RMM:

1. Up to May 2013 (first DHPC and SmPC revision): *reference period*
2. From June 2013 to March 2014 (second DHPC and SmPC revision): *transitional period*
3. And from April 2014 onwards: *assessment period*

Similarly, the study period will be split in two analysis periods for the safety studies:

1. Up to May 2013
2. From June 2013 onwards

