## Safety

1. To estimate the incidence rates of cardiac and thromboembolic events in SR users with and without contra-indications prior and from June 2013.
2. To compare the risk of cardiac and thromboembolic events between new users of SR and new users of oral bisphosphonates without contra-indications, both before and from June 2013.

All of these research objectives will be addressed for the overall eligible population but also after stratification by country, gender, period (three analysis periods (reference, transitional, and assessment) for the assessment of RMM effectiveness, and two periods (before and from June 2013) for the safety studies), month and age, and presence/absence of contra-indications, when applicable/relevant.

In addition, sensitivity analyses excluding participating countries where legal restrictions are in place for the prescription of SR in primary care (i.e. Spain) will be carried out for both the RMM effectiveness and safety studies, and reported accordingly.

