### 9.2.2. Study Period

The study period will start on January 1st 2004 (year of licensing) for all databases except January 1st 2006 for SIDIAP (as data is only available from 2005, and a 1-year washout is required) and will end at the most recent version of data that is available with each of the database custodians.

The study period will be divided into three analysis periods for the assessment of RMM effectiveness: up to May 2013 (*reference* period before first DHPC and revised SmPC), between June 2013 and March 2014 (*transitional* period), and after April 2014 (*assessment* period after second DHPC and new SmPC revision).

As for the safety studies, the study period will be divided in two analysis periods: 1. up to May 2013 (when the first DHPC was published, imposing new contraindications), and 2. from June 2013 (when patients with any of the new contraindications should not be prescribed SR any longer) onwards.

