### 9.5.2. Safety study

Bearing in mind that the number of incident users identified in 2012 is of 5,819 patients, we expect that at least 30,000 incident SR users will be included for the period 2004-2012, and a lower number of people (500 to 1,000 per annum) will be eligible for the prospective cohort of incident users as identified in 2013-2015 due to the DHPC, making a total of 31,500 to 33,000 SR users. With the combined prevalence of exclusion criteria described above (29.5% for men and 19.2% for women) (Abrahamsen, 2014) and a 90% participants being of female gender (based on feasibility counts for 2012 in Table (9.5) 1), a minimum of 25,128 incident SR users would be included. Considering a prevalence of SR use of 20% in osteoporotic treated population, around 125,640 incident bisphosphonate users are expected, making a total of over 150,000 study participants.

We assume a conservative annual incidence rate of acute myocardial infarction of 0.19/100 person-years in the general population of participants in EU-ADR databases (Coloma, 2013). Based on this and assuming an average follow-up period after cohort entry of 2 years we would expect 570 cases. Accepting an alpha risk of 0.05, with 90% power, and a prevalence of SR use of 20% amongst controls, **415** MI cases and a 1:10 case-control ratio (**4150** controls) would suffice to recognize as statistically significant an odds ratio greater than or equal to 1.5. Different scenarios of SR use ranging from 10% to 40% and the corresponding number of MI cases required for an  $OR \geq 1.5$  (at fixed alpha 0.05, power 90%) are shown in Figure (9.5.2) 1.

[figure not shown]
**Figure (9.5.2) 1 - Number of MI cases required to ensure 90% power to detect as significant an  $OR \geq 1.5$  for the association between SR use and MI.**

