### 9.7.4. Pooling

All estimates will be calculated by databases and pooled according to a meta-analysis approach (random or fixed effects model). In addition, to optimize power, we will conduct a mega-pooled analysis, that will estimate the effects putting all individual level data together (fixed and random effects will be checked).

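### The overall (pooled) before/after risk-minimisation proportions compare different country mixes, because Italy is expected to drop out before the assessment period; the database-specific time series are not affected

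*Protocol*

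**What the plan says.** - **Overall results are planned.** Protocol section 8 states, for RMM and safety objectives alike: "All of these research objectives will be addressed for the overall eligible population but also after stratification by country". The RMM objectives use three periods: reference (to May 2013), transitional, and assessment (from April 2014).
- **Pooling.** Section 9.7.4 has estimates calculated per database and combined by meta-analysis. It adds a "mega-pooled analysis, that will estimate the effects putting all individual level data together", with fixed and random effects to be checked. It does not say whether period levels or within-database changes are pooled, or whether database weights stay the same across periods.
- **Italy.** Section 6 says "GPs in primary care are not allowed anymore to initiate or renew strontium ranelate treatment since December 2013" and concludes that "the number of incident strontium ranelate users in the assessment period is expected to be null or very low". The stated response is to look at the point for the first PSUR update. Section 9.3.2 repeats the Italian restriction and describes a milder one in Spain, where GPs may not initiate but may repeat.
- **Spain.** According to the abstract, "the study period will start in 2004 (2006 for SIDIAP) and end at latest data supply".
- **Main RMM method.** Section 9.7.2.2 fits an interrupted time series (ITS) in each data source, with each database as its own control. It also gives prevalences by country.
- **Country-exclusion check.** Section 9.7.5 excludes countries with legal restrictions on primary-care prescribing and names Spain only.

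**The concern.** An overall proportion is a weighted average of country proportions. If a country with a sizeable share is present in the reference period and nearly absent in the assessment period, the average moves whenever that country differs from the others, even if prescribing changes nowhere. The overall change in contraindications, second-line use or severe osteoporosis would then mix the effect of the measures with the loss of Italy, in either direction. The protocol foresees the loss but does not carry it into the pooling rule or the exclusion analysis.

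**Working it through.** **The plan's own precision figures.** n = 1.96² p(1−p)/0.05² gives 319.6 → 320 (p = 0.295), 238.4 → 239 (p = 0.192) and 382.7 → 383 (p = 0.531). All three match section 9.5.1, so 5 points is the right yardstick.

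**Inputs: Table (9.5) 1, SR users in 2012.** The country totals add up to 5,819 incident and 27,764 prevalent users.

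| | Incident | Prevalent |
|---|---|---|
| Italy (HSD) | 1209/5819 = 20.8% | 10129/27764 = 36.5% |
| Spain (SIDIAP) | 4008/5819 = 68.9% | 14502/27764 = 52.2% |
| Spain once Italy is gone | 4008/4610 = 86.9% | 14502/17635 = 82.2% |
| Italy once Spain is dropped | 1209/1811 = 66.8% | 10129/13262 = 76.4% |

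**Effect of Italy's exit.** Hold every country's proportion constant. With Italian weight w, the reference value is w·p(Italy) + (1−w)·p(rest) and the assessment value is p(rest). The spurious change is therefore w × [p(rest) − p(Italy)]. The gap is an assumption:

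| Gap (points) | Incident shift | Prevalent shift |
|---|---|---|
| 0 | 0 | 0 |
| 5 | 1.0 | 1.8 |
| 10 | 2.1 | 3.6 |
| 20 | 4.2 | 7.3 |

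A 5-point shift needs a gap of 5/0.208 = 24.1 points (incident) or 5/0.365 = 13.7 points (prevalent). With equal weights for the five databases, a 10-point gap gives 0.2 × 10 = 2.0 points.

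**Effect of Spain's 2006 start.** Spain contributes to 89 of the 113 reference months. At constant monthly volume its reference share falls from 68.9% to 63.5% (incident) or from 52.2% to 46.3% (prevalent). That is 0.5 to 0.6 point per 10-point gap, much less than Italy.

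**Mega-pooled ITS without database terms.** Illustration: 30% in Italy, 50% elsewhere, no change anywhere, months January 2004 to May 2013 and April 2014 to December 2016, 2012 volumes throughout, Spain absent before 2006 and Italy absent from December 2013.
- Months unweighted: false level change +4.2 points and false slope change −0.07 point per month (prevalent); +0.6 and −0.08 (incident).
- Months weighted by users, with 2004–2005 volume set at 10% of 2012 (a further assumption): +6.9 and −0.008 (prevalent); +3.9 and −0.006 (incident).

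The false slope comes mainly from Spain's late start and nearly vanishes under the second set of assumptions. The false level change from Italy remains.

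**The planned exclusion check.** With Spain dropped, a 10-point gap between Italy and the remaining three databases moves the overall figure by 0.668 × 10 = 6.7 points (incident) or 0.764 × 10 = 7.6 points (prevalent). The check makes the problem larger.

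**After the fix.** If within-database changes are pooled, or weights are fixed over databases present in both periods, the overall change is exactly 0 when no country changes.

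**The case against.** The strongest reply is that the main RMM analysis already works within each database and reports by country, so flat country results would stand beside any shifted overall figure. This stands, and it confines the problem to the overall summaries. A reader might infer that the study's conclusion on RMM effectiveness is invalid. The documents do not support that.

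Second, the meta-analysis sentence in section 9.7.4, applied to ITS estimates, would pool within-database level and slope changes, and a database without assessment-period users would drop out by itself. That is a fair reading for the ITS coefficients. It does not cover the overall period prevalences, to which the same sentence also applies, or the mega-pooled analysis.

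Third, weights and database terms could be left to the statistical analysis plan. Partly so: not mentioning database terms is not the same as specifying a model without them. But the protocol itself states the pooling rule, expects one of its two largest databases to empty, and names only Spain in the exclusion check.

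Fourth, the size depends on gaps that the documents do not give. This stands. The 13.0% to 53.1% range for previous fracture in section 9.5.1 does not fill the hole, since section 7.3 describes both source studies as Danish.

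Fifth, Italy's absence is an expectation, stated for incident users only. For prevalent users it is inferred from the ban on renewals, so the larger figures rest on that inference.

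A reader might also take Spain's late start as an equal cause. The arithmetic shows that it is minor.

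**Conclusion.** The point holds for the overall RMM results only. As written, the plan allows the overall reference-to-assessment contrast to be computed over different country mixes. The resulting artefact is about 2.1 points (incident) or 3.6 points (prevalent) for each 10 points by which Italy differs from the rest, and it is zero if the countries do not differ. At a 20-point gap it is 4.2 or 7.3 points, comparable with the 5-point planning precision.

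These figures assume that the 2012 user counts represent the reference period, that Italy contributes no users from April 2014, and that size-weighted pooling is used. Any fall in Spanish initiations under Spain's own restriction is not modelled and would change the mix further. The change should be made because the overall results answer primary objectives, and the only country-exclusion check is aimed at the wrong country for this purpose.

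**What to change.** - **Sections 9.7.2.2 and 9.7.4:** define the overall RMM effect as the within-database change (reference-to-assessment difference, ITS level and slope). Pool it over databases with users in both periods, using one set of weights. Report HSD separately.
- **Mega-pooled ITS, if kept:** include database-specific intercepts and pre-trends.
- **Section 9.7.5:** extend the exclusion analysis to Italy alone and to Italy plus Spain.
- **Overall period prevalences, if shown:** hold the database (and, if wanted, sex) mix fixed over databases contributing to all periods. Table (9.5) 1 can supply database and sex weights but has no age breakdown. Its prevalent counts by sex should be checked first: HSD gives 613 + 9616 = 10,229 against a total of 10,129, and Aarhus 42 + 412 = 454 against 464.

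The cost is a few sentences and a few lines of code, with no new data. The downside is that the overall contrast no longer covers Italy after December 2013 and leaves out its 36.5% of 2012 prevalent users. The report should say so.

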## 7. RATIONALE AND BACKGROUND

### 7.1. Product

Strontium ranelate (Protelos®/ Osseor®) has been authorized since 2004 in the European Union for the treatment of osteoporosis in postmenopausal women to reduce the risk of vertebral and hip fracture. Since June 2012, strontium ranelate is also approved for the treatment of osteoporosis in adult men at increased risk of fracture. In both indications, the daily dose is 2 g daily (oral). Strontium ranelate is currently authorized in 104 countries and marketed in 91 countries.

### 7.2. Regulatory action

In the frame of 13th PSUR assessment, data submitted raised concern regarding cardiovascular safety beyond the already recognized risk for venous thromboembolism. Analysis of pooled data from randomized studies in around 7,500 post-menopausal women with osteoporosis showed an increased risk of myocardial infarction with Protelos/Osseor as compared with placebo (1.7% versus 1.1 %), with a relative risk of 1.6 (95% CI, 1.07 to 2.38), and an increased risk of venous thrombotic and embolic events — 1.9% versus 1.3 % with a relative risk of 1.5 (95% CI, 1.04 to 2.19).

As a result of this assessment, an increased risk for serious cardiac disorders, including myocardial infarction has been identified and risk minimization measures specifically targeting this identified risk were recommended by the CHMP. These risk minimization measures included a restriction of the target population by excluding patients with established, current or past history of ischaemic heart disease, peripheral arterial disease and/or cerebrovascular disease and/or uncontrolled hypertension, and restricting the indication to severe osteoporosis in postmenopausal women at high risk for fracture to reduce the risk of vertebral and hip fractures and the treatment of severe osteoporosis in adult men at increased risk of fracture. Patients with significant risk factors for cardiovascular events (e.g. hypertension, hyperlipidaemia, diabetes mellitus and smoking) should only be treated with strontium ranelate after careful consideration. In addition, strontium ranelate therapy should only be initiated by a physician with experience in the treatment of osteoporosis. These changes were disseminated in the form of a DHPC in May 2013.

In view of this newly identified risk of serious cardiac disorders, an overall benefit/risk review under Article 20 of regulation (EC) No 726/2004 started in May 2013 and was finalized on 20 February 2014 ([EMA/112925/2014, 2014](#)). This led to a restriction of the indication to patients (postmenopausal women and men) with severe osteoporosis at high risk of fracture for whom treatment with other medicinal products approved for the treatment of osteoporosis is not possible due to, for example, contraindications or intolerance. As part of RMM, a new DHPC was disseminated in March 2014.

Following the outcome of this referral, the MAH has to conduct a non-interventional safety study to evaluate the effectiveness of the applied risk minimization measures.

### 7.3. Observational studies on strontium ranelate use and cardiovascular risk

In the subsequent months, 3 observational studies based on electronic health care databases were published studying the association between strontium ranelate use and cardiovascular risk.

In a nation-wide Danish study by Abrahamsen *et al* (2014), all incident users of SR in the period 2005-2007 in Denmark were identified. In these patients the prevalence of IHD/PAD/CVD (new contraindications) combined was 19.2% in women and 29.5% in men. The risk of myocardial infarction or that of stroke did not differ significantly from other anti-osteoporosis medications, but a 20% increase in all-cause mortality was observed in the group using SR.

A second population-based nested case-control study (Cooper, 2014) used data on women treated with anti-osteoporosis medications in the UK CPRD database between 2002 and April/2012. Amongst 112,445 eligible cohort members, current or past use of SR (compared to no use of SR whatsoever) was not associated with an increased risk of myocardial infarction or cardiovascular death (adjusted OR 1.05, 95% CI [0.68-1.61] and OR 0.96, 95% CI [0.76-1.21] respectively).

Finally, a third study using Danish registers and recently published in the Annals of Rheumatic Diseases (Svanstrom, 2014) has studied the association in women between use of SR and risk of acute coronary syndrome and all-cause mortality using a cohort design. In this case, incident users of SR in 2005-2011 were compared to users of the most commonly used anti-osteoporosis medications (alendronate and risedronate) with similar disease severity. As in the two previous studies, the risk of acute coronary syndrome and death was similar for SR compared to alendronate/risedronate users, with adjusted HR 0.89, 95% CI [0.52-1.55] and HR 0.96, 95% CI [0.76-1.21].

## 8. RESEARCH QUESTION AND OBJECTIVES

This regulatory requested post-authorization safety study will address the following main research questions:

1. What is the effectiveness of the risk minimization measures in different EU member states?
2. Is strontium ranelate associated with an increased risk of cardiac and thromboembolic events?

Therefore, our objectives are:

### PRIMARY OBJECTIVES:

#### Effectiveness of risk minimization

1. To characterise utilization patterns of strontium ranelate in three periods: up to May 2013 (*reference period*), from June 2013 to March 2014 (*transitional period*), and from April 2014 onwards (*assessment period*).
2. To estimate the prevalence of contraindications in SR users during the same three periods: up to May 2013 (*reference period*), from June 2013 to March 2014 (*transitional period*), and from April 2014 onwards (*assessment period*).

3. To calculate the prevalence of SR users who fulfil the new indications (after imposition of new restrictions of use) for SR therapy in these three periods: up to May 2013 (*reference* period), from June 2013 to March 2014 (*transitional* period), and from April 2014 onwards (*assessment* period).

## Safety

1. To estimate the incidence rates of cardiac and thromboembolic events in SR users with and without contra-indications prior and from June 2013.
2. To compare the risk of cardiac and thromboembolic events between new users of SR and new users of oral bisphosphonates without contra-indications, both before and from June 2013.

All of these research objectives will be addressed for the overall eligible population but also after stratification by country, gender, period (three analysis periods (reference, transitional, and assessment) for the assessment of RMM effectiveness, and two periods (before and from June 2013) for the safety studies), month and age, and presence/absence of contra-indications, when applicable/relevant.

In addition, sensitivity analyses excluding participating countries where legal restrictions are in place for the prescription of SR in primary care (i.e. Spain) will be carried out for both the RMM effectiveness and safety studies, and reported accordingly.

## 9. RESEARCH METHODS

### 9.1. Study design

A multinational, multi-database non-interventional population-based cohort design has been chosen as primary design for the assessment of the effectiveness of risk minimization measures.

For the safety study a multinational, multi-database non-interventional nested case control study will be conducted in a cohort of new strontium ranelate or new oral bisphosphonate users.

### 9.2. Setting

This study will be conducted by the EU-ADR Alliance, an academic Alliance of pharmacoepidemiological research institutes in the EU that have decided to collaborate in a distributed fashion to conduct active drug surveillance studies. These institutes have been working together in several EC funded drug safety projects in a similar distributed fashion. Data from the following five European electronic health care databases will be obtained for this study: the Integrated Primary Care Information Project (IPCI) from the Netherlands, the Health Search Database (HSD) from Italy, The Health Improvement Network (THIN) from the UK, the Sistema d'Informació per al Desenvolupament de la Investigació en Atenció Primària (SIDIAP) from Spain, and the Aarhus University Prescription Database from Denmark.

